5 STUDY ENROLLMENT AND WITHDRAWAL

The Pro-GOH target population consists of residents living in buildings housing older adults and disabled adults in Central Connecticut, including the towns of Hartford, New Britain, and Meriden. Based on previous studies in these buildings, we anticipate that the population in the study buildings overall will consist of approximately 40% African American/Caribbean, 45% Latino (mainly Puerto Rican) and 10-15% other ethnic (Euro-American and Polish) residents. Approximately 13% will be under 62 years of age and will have some form of disability. All buildings are located in low income or working class neighborhoods that are medically and socially disadvantaged. Residents often lack access to regular health care and are at high risk for a variety of health and mental health problems.

We will select, match and work in three pairs of buildings of 100 - 250 apartments each. Six buildings have agreed to participate (See letters of support). Our goal in selection of buildings is to achieve a representative sample of residents that approximate the ethnic/racial balance identified above. One building in each pair will be randomly assigned to each condition.

5.1 Subject Inclusion Criteria

Inclusion criteria are:

- a) Disabled children and adults aged 18 years and above, and adults 62 and above, including both male and female building residents, and minorities and non-minorities; restricted to 13.33% under the age of 62 in Cycles II and III by NIDCR as of Oct. 2017.
- b) Permanent residence in sample buildings;
- c) Independent of conservator;
- d) Must be able to speak English or Spanish;
- e) Judged competent to participate (based on ability to respond correctly to key questions about information covered during administration of informed consent.
- f) Have two or more remaining natural teeth.

5.2 Subject Exclusion Criteria

Exclusion criteria are:

- a) Considered by research staff to be cognitively unable to give informed consent;
- b) Exhibition of continued disruptive behavior while participating in the project;

- c) History of infective endocarditis, and/or prosthetic cardiac valve replacement in past 6 months, insertion of an arterial stent in past 6 weeks, myocardial infarction (heart attack) in past 6 weeks;
- d) Under conservatorship;
- e) Fewer than two natural teeth;
- f) Currently on dialysis

5.3 Strategies for Recruitment and Retention

During the first five months of each full intervention cycle 120 residents will be enrolled into the study, 60 in each condition to which their building has been randomly assigned. Research team members will introduce the study in each of the buildings to tenants' associations and onsite managers, soliciting their support for the study. They will conduct 2 presentations 2 weeks apart to inform residents of the study, recruit and enroll potential participants, and within 2 – 3 days schedule appointments to conduct baseline surveys and clinical assessments. Participants will be recruited, enrolled, consented and scheduled for surveys during the first five months regardless of sequence of intervention. Thus, the timing of all surveys and clinical assessments will be the same for both buildings. Research team members will establish a base in a central location in each of the buildings from which to continue recruiting, place informational posters in elevators and in other public locations, actively recruit through engaging people in public spaces, and organizing weekly activities such as bingo games through which recruitment and enrolment will occur. These strategies were very successful in the pilot study. At the same time, 5 - 10 resident volunteers will be invited to join a campaign committee to co-plan and facilitate three building-wide campaigns. Based on prior experience we estimate overall attrition to be approximately 25%.

Retention. Retention in the study will be accomplished:

- a) Through continuous presence in the intervention buildings
- b) Repeated contact through face to face communication and fliers with intervention participants throughout the delivery of each component,
- c) Active telephone and mail reminders in advance of scheduled appointments for surveys, clinical assessments, individual AMI-PM session and campaigns.

We will retain people in the study who, for medical or travel reasons, missed no more than one intervention, one assessment time point, or one intervention and one assessment time point.

Based on prior studies in senior housing, these methods have demonstrated intervention acceptability and are expected to result in almost 100% retention among those residents who are not ill, have not passed away, and have not moved elsewhere.

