5.4.1 Randomization Procedures

Buildings will be paired on the basis of their age, ethnicity and gender characteristics and randomized by a statistician. Individual participants will not be randomized.

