^{**}Sensory impairment (visual or aural) codes: 4 = no sensory problem apparent for either; 3 = some visual or aural impairment; request for repetition of instructions and vocabulary; some difficulty with print size (not related to literacy); 2 = has difficulty hearing and/or can't see instructions at all; 1 = cannot hear sufficiently to respond to a question properly (not a language problem), and/or cannot see enough to recognize the pattern of plaque on teeth (not a comprehension problem).

¹We are measuring oral hygiene skills at T0 – T3, but do not intend to use the results as a mediating measure in accordance with an NIDCR approved request to remove the OH skills assessment as a mediating measure from the study. It was never used as an outcome, but only as a mediator.

12/1/2010

The group level oral health campaign involves volunteer residents as partners in the development of the fairs designed to delivery oral hygiene self-management messages based on the cognitive domains, ADL related problems in brushing and flossing, and brushing and flossing skills, and offer an opportunity to practice brushing and flossing on a mouth model to mastery. To fulfill the requirements of the campaign component of the study (CA), up to three health fairs will be implemented over approximately a three month period. CA+PM procedures include the following:

Identification, Training and Preparation of Pro-GOH Campaign Volunteers. Throughout Condition 1 (AMI-PM+CA+PM) and in the first month of Condition 2 (CA+PM+ AMI-PM) the study team will recruit 5-10 building residents to facilitate the group intervention. The committee will include building residents as role models who are broadly representative of the composition of the building by age, ethnicity, gender, ability and language. All committees will have bilingual (English/Spanish) capacity. Once recruited, consented and enrolled, committee members will meet with study trainers for 2-hour sessions twice a week, for a minimum five to six week period, to learn how to implement pro-oral health campaigns, to plan for each fair and to work with study interventionists to develop campaign materials. The Pro-GOH campaign events follow primary communications principles:

- a) Message redundancy: same message delivered through different materials (at least 4 different types of materials in English and Spanish),
- b) Multiple channels (messages delivered through oral, visual, written and practice means)

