15.3 Informed Consent Process

Informed consent is a process that is initiated prior to the individual agreeing to participate in the study and continues throughout study participation. Extensive discussion of risks and possible benefits of study participation will be provided to subjects and their families, if applicable. A consent form describing in detail the study procedures and risks will be given to the subject. Consent forms will be IRB-approved, and the subject is required to read and review the document or have the document read to him or her. The investigator or designee will explain the research study to the subject and answer any questions that may arise. The subject will sign the informed consent document prior to any study-related assessments or procedures. Subjects will be given the opportunity to discuss the study with their surrogates or think about it prior to agreeing to participate. They may withdraw consent at any time throughout the course of the study. The rights and welfare of the subjects will be protected by emphasizing to them that the quality of their clinical care will not be adversely affected if they decline to participate in this study. We also will repeat screening for the eligibility criteria.

All individuals will be consented by trained survey or clinical assessors in the study. Participants will be asked to respond to 5 key questions to evaluate whether they understand the purpose of the study, what activities their participation entails, risks that might be encountered, expected duration of participation, and whether participation is voluntary.

Two copies of the consent form will be signed and dated by participant and assessment administrator. One is kept in the participant's hard copy file, and scanned for electronic warehousing, and the second is given to the participant.

A record of consent administration by date will be kept in the participant's access form, data to be entered by the survey coordinator.

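### Buildings are assigned before residents are recruited and no section conceals the condition during the five-month enrolment window, so who joins and how T0 is scored can differ by condition

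*Combined protocol and SAP*

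**What the plan says.** Section 5.3 places enrolment in the first five months of each cycle, during which "120 residents will be enrolled into the study, 60 in each condition to which their building has been randomly assigned". Section 5.4.1 says "Buildings will be paired on the basis of their age, ethnicity and gender characteristics and randomized by a statistician", and adds that individual participants are not randomised.

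Recruitment is active. Research staff take a base in the building and "actively recruit through engaging people in public spaces, and organizing weekly activities such as bingo games" (Section 5.3). On consent, Section 15.3 says "All individuals will be consented by trained survey or clinical assessors in the study". The enrolment window is common to both conditions: "Participants will be recruited, enrolled, consented and scheduled for surveys during the first five months regardless of sequence of intervention" (Section 5.3).

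Section 6 says that campaign committee recruitment goes on throughout Condition 1 and "in the first month of Condition 2 (CA+PM+ AMI-PM) the study team will recruit 5-10 building residents". Section 5.3 describes inviting volunteers at the same time as enrolment and does not distinguish the conditions.

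Section 8.1 keeps the survey coordinator out of the intervention. No section says that recruiters, residents or T0 examiners are kept unaware of the building's condition.

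**The concern.** In a cluster trial, randomising the buildings balances (on average) the people who live in them. It does not balance the people who later agree to join, if the condition is known while they are being approached. Recruiters who know which component comes first can vary whom they approach or how they describe the study, and residents can respond to the order on offer. T0 examiners who know the condition can also score differently, which would weaken T0 as an adjustment variable.

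The comparison at stake is Hypothesis 1, AMI-PM against CA+PM at T1. Section 12.2 powers the trial on it, and Section 12.4 analyses it by standard methods for a parallel two-arm randomised study. The Hypothesis 2 contrast uses the same enrolled samples.

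**Working it through.** **1. Order of events.** Section 5.3 speaks of a building that has already been assigned when its residents are enrolled. Section 5.4.1 makes the building the only randomised unit. Sections 5.3, 5.4, 7.1, 8.1 and 15.3 contain no concealment step.

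**2. What can disclose the condition during enrolment** (five months, taken as about 150 days):
- Staff knowledge of the assignment, from the first day.
- AMI-PM sessions in AMI-first buildings, due within 45 days of each person's T0 (Section 6, Appendix A). They can begin while about 150 − 45 = 105 days of enrolment remain.
- Committee training, at least five to six weeks of twice-weekly meetings once members are recruited (Section 6). Its timing follows the sequence.
- Fairs in campaign-first buildings, 3-6 months after study entry (Appendix A). Counted from the first entry, this is about day 90 to 180 and overlaps the last 150 − 90 = 60 days.

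**3. What does not disclose it.** An invitation to join the committee. Sections 5.3 and 6 together put invitations in both conditions.

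**4. Sensitivity of the planned test.** The plan's lowest power figure comes first: Plaque Index, difference 0.20, SD 0.47, 123 per group, two-sided 0.05 (Section 12.2).
- Effect size 0.20/0.47 = 0.426 (table: 0.42).
- Noncentrality 0.426 × √(123/2) = 3.34.
- Power 91.6% (normal) or 91.4% (noncentral t), against 91% stated. The figure reproduces.

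Now set the true effect to zero and let recruitment leave a difference of b SD at follow-up. The value of b is an assumption; the documents give none. The plan's 123 per group is taken as given, and the comparison is unadjusted.

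| Assumed b (SD) | On plaque scale (b × 0.47) | False-positive rate | Power if b opposes the planned 0.20 |
|---|---|---|---|
| 0.05 | 0.02 | 6.8% | 83% |
| 0.10 | 0.05 | 12.2% | 72% |
| 0.20 | 0.09 | 34.6% | 42% |
| 0.30 | 0.14 | 64.9% | 17% |

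If only half of a 0.20 SD T0 difference carries to follow-up, the false-positive rate is 12.2%. The table shows how sensitive the test is. It is not evidence that such a difference exists.

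**5. What later allocation could conceal.** If the first T0 is near the start of the cycle, the draw can wait until about day 45, which covers 45/150 = 30% of the window. Six weeks of committee training after that ends at about 45 + 42 = day 87, just before the fair window opens at about day 90. The existing windows can therefore be kept.

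**The case against.** Three stronger readings are tempting, and the documents support none of them.

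- *Committee recruitment in month one reveals a campaign-first building.* It does not by itself. The same sentence in Section 6 has committee recruitment throughout Condition 1, and Section 5.3 invites volunteers without distinguishing conditions.
- *A private session and a public fair attract different people.* Every participant is offered both, with the same T0 tasks and payments (Appendix A), and the campaign is open to all residents whether enrolled or not (Section 6). Only the order differs, and nothing in the documents shows that order affects willingness to join.
- *The enrolled samples did differ, or staff and residents were told the condition.* The documents say neither. They state no concealment, and the manual of procedures that Section 7.2 points to was not available.

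There are also real limits on selection. Buildings are paired on age, ethnicity and gender. The recruitment window is common to both conditions. Cycles II and III have a quota for those under 62 (Section 5.1), and screening uses an approved script (Section 7.1). Sixty enrollees in buildings of 100-250 apartments (Section 5) equal 60/250 = 24% to 60/100 = 60% of apartments, which narrows the room to steer. Section 12.4 recognises that individuals are not randomised and expects to adjust.

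These points reduce the likely bias and they stand. They do not close the gap. Pairing does not use oral hygiene or motivation, a common window equalises timing but not knowledge, and the adjustment in Section 12.4 is described only as likely. Its list of covariates includes self-assessed oral health but does not name T0 Plaque Score or Gingival Index.

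**Conclusion.** The point holds as a design weakness. Followed as written, the plan leaves the powered T1 contrast open to recruitment after a known allocation, and adjustment can remove only the measured part. The mechanism is moderate: the incentive to self-select concerns order alone, and the more direct route is staff who know the assignment.

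The size cannot be estimated from the documents. The error rates above rest on assumed differences of 0.05 to 0.30 SD, an unadjusted comparison and the plan's own 123 per group. The conclusion also assumes that no unseen manual already imposes concealment. It is worth correcting because the change is cheap and bears on the primary contrast.

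**What to change.** For any cycle not yet enrolled:
- Draw each pair's allocation after the introductory presentations and as much T0 enrolment as the schedule allows, at the latest just before the first AMI-PM session falls due. Bring recruitment and T0 forward into that period.
- Run committee invitations identically in both buildings until release, and align the committee timing in Section 6 with this.
- Have the statistician release the result to intervention staff only. Use one recruitment script that does not state component order.
- In Section 12.4, replace the tentative adjustment with a stated one for T0 Plaque Score and Gingival Index. Compare, by building, the T0 scores of residents enrolled before and after release. With six buildings this comparison is descriptive.

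For cycles already enrolled (this version is dated December 2018), only the T0 adjustment remains, with reporting of T0 scores and whatever recruitment counts exist by building.

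The cost is protocol wording, a sealed release and shorter notice to intervention staff of which component starts first. Visit windows need not change. The gain is limited: about 30% of the enrolment window is concealed, and later enrollees can still infer the condition once sessions or training begin.

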5.5.2 Handling of Subject Withdrawals or Subject Discontinuation of Study Intervention

The sample size was powered anticipating an attrition rate of 25% which greatly exceeds our experience in the pilot study which was 15%. We do not expect people to withdraw because of adverse effects of the interventions. Once we are certain at any point in time that a participant has withdrawn or has discontinued, we will retain the person in the study up to the point at which they have withdrawn. If they withdraw after T1, we will include them in the T1 comparison. If they withdraw after T2 and before T3, we will include them in the T2 analysis, but exclude them from the T3 sustainability of effect analysis.

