12 STATISTICAL CONSIDERATIONS

12.1 Study Hypotheses

- 1. The AMI-PM will produce better short term (T1) clinical outcomes than the Campaign (CA+PM) (AIM 1).
- 2. The CA+PM+AMI-PM will produce better mid-term (T2) and long-term (T3) clinical outcomes than the AMI-PM+CA+PM (AIM 2).
- 3. The AMI-PM will produce more change in mediating cognitive domains than the CA+PM.
- 4. Both AMI-PM+CA+PM and CA+PM+AMI-PM will result in no differences in change in mediating cognitive domains from T0 to T2.
- The greater the dosage (proportion of total talking points recorded for all domains in a tailored AMI; and exposure to campaign activities and messages), the better the outcomes.
- 6. We will investigate an exploratory hypothesis examining the effects of the intervention and sequence on oral health quality of life (a secondary outcome), as well as on clinical outcomes.

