12.4 Final Analysis Plan

The usual inspection for outliers and influential data points will be conducted along with summary statistics and evaluations of distributions of the data. We have experience with the clinical outcome measures, which have approximately normal distributions. In the case of non-normal data, we will use standard transformations (e.g., log) or explore alternatives (e.g., non-parametric approaches or other distributions such as Poisson).

Period 1: parallel arm phase: Standard approaches for a parallel 2-arm randomized study will be conducted for the first period of the sequence, across all buildings. This analysis allows direct comparison of the AMI vs. the Campaign approach for clinical outcomes (Study Hypothesis #1).

Periods 1 and 2: assessing sequence of interventions: Study Hypothesis #2, which sequence gives better clinical outcomes, will be addressed using repeated measures models. Depending on whether the outcome is continuous or dichotomous, we use general linear mixed models (GLMM) or general estimating equations (GEE), respectively, to fit a model with intervention and period effects using the MIXED procedure in SAS®. Each set of measures from the same person (e.g., gingival outcomes) are treated as a correlated cluster of data. An AR-1 correlation structure is

likely to be appropriate. Customized contrasts can be constructed to make comparisons

between time points. Time-varying covariates can be used in these models, and some missing data (under MAR or MCAR assumptions where applicable), is allowable.

Baseline & health status variables: As this study randomizes at the level of site and individuals are not randomized, we will likely stratify some results (or adjust in models) for demographics such as age, gender, marital status and individual characteristics such as health status, ADLs, depressive symptoms (CES-D) and oral health status (self-assessment). Any variable that shows potential for confounding or effect modification will be accounted for appropriately in all stages of the analysis.

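### The retention sentence in section 5.3 implies dropping people by attendance and reason after building randomisation, and nothing in the plan provides for following them or says how they are analysed

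*Combined protocol and SAP*

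**What the plan says.** The retention part of section 5.3 sets a condition for staying in the study: "We will retain people in the study who, for medical or travel reasons, missed no more than one intervention, one assessment time point". A single miss of each kind is also tolerated. The sentence names two permitted reasons and a limit on the number of misses.

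The condition can only operate after allocation. Section 5.3 describes enrolment as "60 in each condition to which their building has been randomly assigned", and section 5.4.1 adds: "Individual participants will not be randomized".

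Section 5.5.2 deals with people who withdraw or who discontinue the intervention: "we will retain the person in the study up to the point at which they have withdrawn". Those leaving after T1 count in the T1 comparison. Those leaving between T2 and T3 count at T2, "but exclude them from the T3 sustainability of effect analysis".

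For the repeated-measures models, section 12.4 says that "some missing data (under MAR or MCAR assumptions where applicable), is allowable". It names no intention-to-treat or other analysis population. Hypothesis 5 in section 12.1 concerns dosage of both components and ends "exposure to campaign activities and messages), the better the outcomes".

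**The concern.** Attendance is behaviour seen after allocation, and it is plausibly related to oral hygiene. If people leave follow-up because they did not attend, those who remain at T2 and T3 are a selected group. If the selection differs between conditions, the comparison of sequences is no longer protected by the building randomisation alone.

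There is a reason to expect some difference. In Condition 1 the first component is one scheduled individual session. In Condition 2 it is a series of group fairs on fixed dates. The opportunity to miss, and the way staff would count a miss, are not the same.

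Hypothesis 5 is also affected. It needs people with little exposure. If low attenders stay only when their reason is illness or travel, the low-dose group becomes smaller and tilts towards people who are ill or away.

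**Working it through.** **1. The plan's own figures.** Sections 4 and 12.2 assume 75% retention: 360 × 0.75 = 270 in total, 180 × 0.75 = 135 per condition, 60 × 0.75 = 45 per building. All three reproduce. They do not separate people who are lost from people not retained under the attendance sentence. The smallest planning effect in the section 12.2 table is 0.20 / 0.47 = 0.426 SD (printed as 0.42).

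**2. Whom the sentence can exclude, and when.** This follows from the wording and the Appendix A schedule.

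- *T1, if an intervention means a component.* Each condition has been offered one component and T1 is the first follow-up. Nobody can have missed more than one of each, so only the reasons clause can exclude anyone.
- *T1, if each fair counts.* A Condition 2 resident who misses two of the three fairs is over the limit before T1. A Condition 1 resident has been offered only one session and cannot be.
- *T2 and T3.* Both components have been offered and two or three follow-up assessments have fallen due. The numerical limit can now act in both conditions, alongside the reasons clause.

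A related gap is that Appendix A times T1 in Condition 1 from the individual session, so a resident who skipped it has no defined T1 date. In Condition 2, T1 is timed from completion of the campaigns, so a non-attender still has one.

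**3. Does another section cancel it?** Section 5.5.2 preserves earlier data, which limits the damage, but it does not call for further assessments. The missing-data statement in section 12.4 is attached to the repeated-measures models. It describes what those models tolerate and does not say who is followed or in which condition they are analysed.

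**4. Size, for scale only.** The documents give neither the share removed nor its relation to outcome, so both are assumptions. Suppose adherence and outcome are jointly normal with correlation c, and the least adherent fraction x is removed. The mean of those kept shifts by c·φ(z) / (1 − x) SD, where z is the x-quantile of the standard normal. With c = 0.3:

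- x = 0.05: 0.3 × 0.1031 / 0.95 = 0.033
- x = 0.10: 0.3 × 0.1755 / 0.90 = 0.059
- x = 0.15: 0.3 × 0.2332 / 0.85 = 0.082

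The shift in the difference between conditions is the gap between the two arms:

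- 15% against 5%: 0.082 − 0.033 = 0.05 SD
- 15% against 10%: 0.082 − 0.059 = 0.02 SD
- equal shares of similar people: 0

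Against 0.42, these are about 12% (0.05 / 0.42) and 5% (0.02 / 0.42) of the planning effect.

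A cruder check assumes that people removed differ from those kept by 0.5 SD. The shift is then the difference in shares times 0.5: 15% against 5% gives 0.10 × 0.5 = 0.05 SD, and a wider gap of 25% against 10% gives 0.15 × 0.5 = 0.075 SD.

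**The case against.** The strongest reply is that the sentence is a tolerance and not an exclusion. It sits among retention strategies, shortly before an expectation of near-complete retention of residents who have not fallen ill, died or moved. No passage says that others are refused assessment or have data deleted. This stands in part: removal is implied, not written. But the sentence sets conditions, and even on the lenient reading the plan does not say what happens to people outside them.

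Four stronger conclusions are tempting, and the documents do not support them.

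- *That the trial becomes a comparison of adherent participants.* Section 5.5.2 covers discontinuation as well as withdrawal and keeps data already collected. The study is powered on period 1, where on the component reading only the reasons clause can act.
- *That the two conditions must lose different people.* By T2 both have been offered the same two components under the same rule. Order and the counting of fairs could still produce a difference, but the documents do not show one.
- *That the bias is a large share of the planning effect.* Shifts of 0.08 SD (15% removed, correlation 0.3) or 0.14 SD (20% removed, correlation 0.4) arise only if one condition loses people and the other loses nobody.
- *That Hypothesis 5 loses its low-dose participants.* Those with one medical or travel miss are kept, and dose is graded among attenders by talking points covered and campaign exposure.

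**Conclusion.** The point holds as a gap in the plan. The attendance condition acts after building randomisation, its unit is undefined, and neither section 5.5.2 nor section 12.4 supplies continued assessment or an analysis population. Followed literally, it could select participants differently in the two conditions. On the component reading, the exposure at T1 is confined to the reasons clause; it is wider at T2 and T3, the time points that Hypothesis 2 uses.

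The magnitude is unknown. The range of about 0.02 to 0.05 SD rests on an assumed correlation of 0.3 and assumed removal of 15% against 5% to 10%. Balanced removal of similar people would give no bias, and a wider imbalance would give more. This is worth correcting because the remedy is simple, not because a large distortion has been shown.

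**What to change.** Replace the retention sentence in section 5.3. Every consented participant with a T0 assessment is invited to all later assessments whatever interventions or visits were missed, unless consent is withdrawn. Say when T1 or T2 falls for someone who missed the session from which it is timed.

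In section 12.4, state that the primary analyses include all these participants in their building's assigned condition, using all available data. Define one intervention, record missed components as dosage, and restrict attendance-based sets to Hypothesis 5 or a labelled per-protocol sensitivity analysis. Align section 5.5.2 so that stopping an intervention does not end assessment.

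The cost is protocol and SAP wording, some reminders and the assessment payments. From Appendix A, full follow-up after T0 pays at most 15 + 15 + 15 + 15 + 20 = $80 per person. If, as an assumption, 10% of the 360 were kept who would otherwise be dropped, that is at most 36 × 80 = $2,880.
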